2. STUDY OBJECTIVES

The broad objective of this exploratory, observational, study is to characterize upper GI symptoms in subjects with CV risk or confirmed disease taking LDA for primary or secondary cardiovascular disease prevention. More specifically, the study will:

[figure not shown]
- Characterize the frequency and nature of the upper GI symptoms
- Observe and record upper GI symptoms and compliance with LDA, and other relevant medications.
- Document the subject's behaviour, subjective experience, and evaluation of their condition (e.g., sleep, GI events, doctor's visits, etc.).

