3.4.1 Visit Procedures

3.4.1.1 Visit 1

Subjects visiting their physician for a “usual care” visit will be asked if they would like to participate in the study. They will be informed of the nature of the study and the requirements and that each component of the study will occur in succession and that they may not qualify for all stages.

If subjects choose to participate, they will be asked to read and sign an informed consent. Basic demographic and medical information will be collected by the Investigator or a designee using a paper CRF. Subjects will then complete the survey utilizing an electronic SitePro device while still at the investigative site. Questions will include, but will not be limited to: upper GI symptoms, LDA use, medication taking behaviour and other information relevant to the objectives of the study. The specific domains that will be assessed, and the actual items of the survey are listed in Section 4.2.1, and Appendix C. Additional information will be captured by the investigator using a paper CRF.

Following completion of the survey, the SitePro device will apply a preset eligibility algorithm to a subject's data and determine eligibility for one of the 3 Diary/EMA groups. Once eligibility is confirmed following review by the investigative site staff, the subject will be invited to participate in the Diary/EMA phase of the study. Subjects who are not eligible will be thanked for their time and then discontinued from the study.

[figure not shown]
Subjects who agree to participate in the Diary/EMA phase will then be trained on the procedures and the use of the ePRO diary device by the investigative site staff. Training on

the ePRO will follow a standardized training program and include both printed materials and hands-on activities on the ePRO device itself.

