Once trained, subjects will be sent into the field to capture data on a daily basis using the ePRO device. Each day the ePRO device will prompt (via an audible alarm) the subject three (3) times each day and administer questions regarding the subject's experience with LDA. In particular, the ePRO device will ask subjects about upper GI symptoms, medication use, and about their daily activities and mood. The ePRO-EMA diary-assessment is outlined in Section 4.2.2, specific questions are listed in Appendix D. Additionally, subjects can make entries into the ePRO device at any time about any discrete episode of UGI symptoms that they experience. Upon making an entry, the device will administer questions about the nature of the episode.

The structure of how the ePro diary device will prompt the subject over the course of a day is depicted below.

Figure 2 ePRO Device daily window schematic

Delay Feature will be available for Morning, Afternoon, Evening Report alarms.

After following these daily procedures, the subjects will put the ePRO device onto a charging device that also contains a modem to transfer data. Each night, the device will automatically (without subject intervention) utilize the modem to transfer the subject's data to a central data server. The investigative site staff will be expected to review subject compliance with EMA procedures utilizing web access to the data on the central server.

Between this and the next visit, the investigative site may be contacted by a Clinical Research Associate (CRA) if individual subjects are not compliant with the EMA procedures.

3.4.1.2 Visit 2

Approximately 45 days after Visit 1, subjects will return for a review of their compliance with the Diary/EMA procedures. During this visit, the investigative site staff will transfer data

from a subject's ePRO device to the central data server. A review of the subject compliance with the Diary/EMA procedures will then be performed utilizing a web access to the data. Subjects who are not complying with procedures will be given feedback, asked if they are experiencing specific problems, and then asked to comply with procedures for the remainder of the EMA period.

Subjects will be subject to the usual clinical care of the investigative site. No procedures beyond the compliance review are required.

Between this and the next visit, the investigative site may be contacted by a CRA if individual subjects are not compliant with the EMA procedures.

3.4.1.3 Visit 3

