Overall feeling?	Very bad, Bad, Neutral, Good, Very good
Arousal/energy level?	Very low, Low, Moderate, High, Very high
Thank you!	

Evening Assessment

Text	Response options
Answer the following about the time since your last evening report...	
Since last evening report	
What medications did you take?	Low dose aspirin, Other heart medication, GI medication
Did you visit the doctor or hospital?	Doctor, Emergency room, Hospital
Was it a planned visit?	Yes, No
Are you still in the hospital?	Yes, No
Why did you visit the hospital or doctor?	Heart related problems, GI problems, other
Able to control important things?	NO!!, no??. yes??. YES!!
Able to handle personal problems?	NO!!, no??. yes??. YES!!

Nervous/stressed?	NO!!, no??. yes??. YES!!
Things going your way?	NO!!, no??. yes??. YES!!
Unexpected event upset you?	NO!!, no??. yes??. YES!!
Upset by things out of your control?	NO!!, no??. yes??. YES!!
Since last report	
Did you experience a GI episode?	Yes, No
Where were you most?	Home, Workplace, Other's home, Bar, Restaurant, Vehicle, Outside, Casino, Other

What were you doing?	Working/chores, Inactive/leisure, Interacting with others, Eating/drinking (15 min), Between activities, Other activities
Type of work?	Job, School, House/Personal, Other
Type of inactivity/leisure?	Media, Hanging out, Hobbies, Sports/Exercise, Reading, Waiting, Doing nothing, Other
Type of interaction with others?	Socializing, For business, Household issues, Arguing, Other interaction
What eating or drinking?	Meal, Snack, Caffeinated drink, Non- caffeinated drink, Alcohol
Thinking about your emotions since your last report...	
Able to focus?	NO!!, no??. yes??. YES!!

Alert?	NO!!, no??. yes??. YES!!
Angry/frustrated?	NO!!, no??. yes??. YES!!
Bored	NO!!, no??. yes??. YES!!
Calm/relaxed?	NO!!, no??. yes??. YES!!
Difficulty concentrating?	NO!!, no??. yes??. YES!!
Enthusiastic?	NO!!, no??. yes??. YES!!

Happy?	NO!!, no??. yes??. YES!!
Irritable?	NO!!, no??. yes??. YES!!
Miserable?	NO!!, no??. yes??. YES!!
Nervous/tense?	NO!!, no??. yes??. YES!!
Quiet/sleepy?	NO!!, no??. yes??. YES!!
Restless?	NO!!, no??. yes??. YES!!

Sad?	NO!!, no??. yes??. YES!!
Overall feeling?	Very bad, Bad, Neutral, Good, Very good
Arousal/energy level?	Very low, Low, Moderate, High, Very high

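### The evening diary cannot mark the Day 45 study visit, so healthcare use can gain up to one study-generated doctor visit per subject

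*Protocol*

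**What the plan says.** The third specific objective (Protocol section 2) is to document the subject's behaviour, "subjective experience, and evaluation of their condition (e.g., sleep, GI events, doctor's visits, etc". Table 3 (section 4.2.2) lists healthcare utilization as a diary variable, collected only in the evening report.

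The Evening Assessment (Appendix D) opens with "Answer the following about the time since your last evening report" and then asks "Did you visit the doctor or hospital". The answers are doctor, emergency room or hospital. Follow-up items ask "Was it a planned visit" and the reason, with the options "Heart related problems, GI problems, other". There is no study-visit answer and no instruction to leave study visits out.

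The visits are set out in section 3.4:

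- **Visit 1 (Day 1):** "Subjects visiting their physician for a “usual care” visit will be asked if they would like to participate in the study".
- **Visit 2 (Day 45 ± 7):** "subjects will return for a review of their compliance with the Diary/EMA procedures". Site staff transfer the data and review compliance. The study requires nothing more, although usual care may also be given.
- **Visit 3 (Day 90 ± 7):** the same review, after which the device is handed back.

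Section 3.3.1 recruits subjects through their own primary care physician, cardiologist or practice group.

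**The concern.** Visit 2 exists only because of the study, yet it takes the subject to their own doctor's practice on a day the diary covers. Doctor is then a fair answer that evening. The follow-up items do not isolate the visit: a scheduled usual-care visit is also planned, and the other category holds all care that is neither cardiac nor GI.

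A count of doctor visits from the diary would then mix care the subject sought or needed with attendance set by the protocol. The bias is upward. The extra entries follow the study calendar rather than symptoms, so they would also add noise to any analysis that relates symptoms to all planned doctor visits.

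**Working it through.** The protocol states no visit rate and no utilisation endpoint, and section 6.1 makes no formal sample size calculation. There is therefore no figure of the plan's own to reproduce for this item. The current group targets (Amendment 2, revised section 3.1) do add up: 200 + 25 + 50 = 275 with data, and 240 + 30 + 60 = 330 enrolled.

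**Step 1. Which visits can produce a study-generated entry?** Two conditions are needed: the study creates the visit, and an evening report follows it.

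| Visit | Created by the study? | Evening report afterwards? | Study-generated entry possible? |
|---|---|---|---|
| Visit 1, Day 1 | No, recruitment is at a usual-care visit | Possibly | No |
| Visit 2, Days 38 to 52 | Yes | Yes | Yes |
| Visit 3, Days 83 to 97 | Yes | No, device collected | No |

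Only Visit 2 qualifies, so the excess is at most 1 entry per subject. The ceiling is 275 × 1 = 275 entries at the data target, or about 330 if every enrolled diary subject attends.

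A missed report on the evening of Visit 2 does not necessarily lose the entry, because the next report looks back to the last one completed. Section 3.3.6.1 also makes completing fewer than 80% of evening reports a reason for discontinuation, so capture among retained subjects should be high.

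**Step 2. Relative inflation of the doctor-visit rate.** Let k be the genuine doctor visits per subject in three months, and p the share of subjects who log Visit 2 as a doctor visit. Both are assumptions.

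Recorded rate = k + p. Relative inflation = p / k.

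| k | p = 0.25 | p = 0.5 | p = 1 |
|---|---|---|---|
| 0.5 | 0.25/0.5 = 50% | 0.5/0.5 = 100% | 1/0.5 = 200% |
| 1 | 0.25/1 = 25% | 0.5/1 = 50% | 1/1 = 100% |
| 2 | 0.25/2 = 12.5% | 0.5/2 = 25% | 1/2 = 50% |

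**Step 3. Where the excess falls.** A compliance visit is planned, is not an emergency-room or hospital visit, and is most naturally coded as other. The excess therefore sits mainly in planned doctor visits with reason other. Some leakage into heart or GI reasons is possible, because the list has no fitting answer for a subject attending a cardiology practice for a GI-symptom study.

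**The case against.** The strongest case for leaving this alone has four parts.

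- **Visit 2 is a staff check of a device.** No physician contact is required, so many subjects may not call it visiting the doctor. Some leave before Day 45, and some receive genuine care at that visit. This stands. It is why p must be varied, and why 275 is a ceiling and not an estimate.
- **The follow-up items contain the damage.** This largely stands. Unplanned and GI-reason visits bear most directly on GI burden, and they should be little touched. Planned doctor visits are not protected.
- **Doctor visits are one example in the third objective of an exploratory study without hypothesis tests.** This is true, and it limits the importance. Healthcare utilization is nevertheless a listed diary variable with its own items.
- **Visit 2 is dated, so the SAP can remove its entries.** Section 6.2 leaves specific analyses to a SAP that was not available here. A date rule is only a partial repair, because it cannot separate a study-only attendance from usual care given at the same visit. The item's wording is fixed in the protocol.

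A reader might go further and infer two study entries per subject (2 × 275 = 550), inflation for every diary subject, or a share with any doctor visit that approaches 100% by design. The documents do not support these readings. Counting two entries requires Visit 1 or Visit 3 to qualify, but Visit 1 is usual care that the study did not create, and Visit 3 ends with the device being returned. The other two readings require almost every subject to log Visit 2 as a doctor visit, or Visit 1 to be counted as study-driven, and the protocol establishes neither.

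**Conclusion.** The point holds for Visit 2 only. As worded, the evening item can record the Day 45 compliance visit as a planned doctor visit, and the diary has no way to tell it from care. The excess is at most one entry per subject over three months, and at most about 275 entries at the current data target.

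Across the assumed range of 0.5 to 2 genuine visits, the doctor-visit rate is inflated by 50% to 200% if all subjects log Visit 2, and by about 12% to 50% if a quarter do. These percentages rest on assumed visit rates and an assumed logging share, neither of which the protocol gives. The direction of the bias and the one-entry ceiling come from the text itself.

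This is a modest defect in one descriptive domain, worth correcting because the correction is nearly free.

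**What to change.** **Diary text.** Begin the item with *Other than visits made only for this study*, and leave the rest of the question unchanged. The word *only* keeps genuine care given on the same occasion. The cost is one phrase on the device.

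**Data already collected.** Flag planned doctor entries in the first evening report completed after Visit 2, and report utilisation with and without them. Using the first completed report, rather than only the visit date, also catches entries made after a missed evening. The cost is one derivation rule based on visit dates that the sites hold. The small downside is that genuine usual care given at Visit 2 drops out of the version with removal, so both versions should be shown.

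**Visit 1.** Do not remove its entries as study visits, since that would delete genuine care. If Day 1 reports capture it, treat it as the index visit and start the prospective count after Visit 1, as a sensitivity analysis.

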3. STUDY PLAN AND PROCEDURES

3.1 Design and study flow synopsis

This is an observational study design delivering up to 15 months of data of which 12 months are retrospective and 3 months prospective. It consists of three stages: a one-time, cross-sectional survey; a prospective, three month diary; and, a personal (cognitive) interview. All data will be captured from subjects in the context of their usual care for CV disease or risk, that is, there will be no study treatment or intervention. Figure 1 is a graphical summary of the three stages.

Figure 1 **Flow Chart**

In the first stage of the study, approximately 2,000 subjects who have been prescribed LDA usage in the past 12 months, or those about to begin LDA, will complete a one-time in-office survey using an electronic personal digital assistant (PDA) device (termed SitePro). The survey will ask subjects about:

- Use of LDA (75-325 mg daily);
- subject’s experience, if any, of UGI symptoms during the time they were using LDA;
- the impact of UGI symptoms on the subject’s compliance with taking LDA and medications related to their CV disease or CV risk factors;
- background information about subject’s emotional state and well being.

The specific domains that will be assessed, and the actual items of the survey are listed in Section 4.2.1, and Appendix C. Additional information such as medical history and concomitant medications will be captured by the investigator using a paper CRF.

A subset of the subjects of whom all complete the survey will be invited to participate in a three (3) month prospective diary period where real-time assessments will be administered using the ecological momentary assessment (EMA) approach. Four hundred, twenty (420) subjects stratified into three groups varying on length of time using LDA will be asked to use

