an electronic PRO device (ePRO) to record information about their experience with LDA for the period of 3 months. The ePRO device will prompt (via an audible alarm) the subject three (3) times each day and administer questions regarding the subject's experience with LDA. In particular, the ePRO device will ask subjects about UGI symptoms, medication use, and about their daily activities and mood. The areas of assessment are listed in Section 4.2.1 (Table 2), and the specific questions are listed in Appendix D. The goal is to obtain EMA data from 350 subjects in the three groups: 200 Naïve LDA users (240 enrolled) who begin LDA use at the time of the study; 100 Short-term LDA users (120 enrolled); and, 50 Long-term LDA users (60 enrolled). A detailed description of the inclusion/exclusion criteria for each EMA group can be found in Section 3.3.3.

Finally, a sample of up to 20 subjects from the three EMA groups will be interviewed (see Section 3.3.4) to further debrief their experience with LDA and upper GI symptoms. This 1 hour cognitive interview will include the following areas:

- the subject's experience with upper GI symptoms;
- the subject's use of and compliance with LDA and other CV related medication;
- the subject's perceived impact of upper GI symptoms on their ability to continue with medication;
- the broader impact of these symptoms on their life.

The subjects will be selected following review of Diary/EMA data, and investigators will be asked to invite selected subjects to participate in these interviews.

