3.3.2 Survey inclusion/exclusion criteria

3.3.2.1 Inclusion criteria

- Provision of signed written informed consent.
- Female or male aged 18 years and over.
- Physician prescribed or recommended daily intake of LDA (75-325 mg daily) for cardiovascular disease prevention within the past 12 months, including the day of entry into the study.
- Established cardiovascular disease, such as (but not restricted to) CAD (Coronary Artery Disease), previous TIA (Transient Ischemic Attack) or ischemic stroke (secondary prevention), or subjects with known risk factors for cardiovascular disease without having experienced cardiovascular events previously (primary prevention).
- In the judgement of the investigator, the subject is able to carry out the procedures required by the CSP.

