1.7 Morisky Medication Taking Behavior Scale

Morisky Medication Taking Behavior Scale

1. Do you sometimes forget to take your CV medications? (Check one)

Yes

No

2. People sometimes miss taking their CV medications for reasons other than forgetting. Thinking over the past two weeks, were there any days when you did not take your CV medications? (Check one)

Yes

No

3. Have you ever cut back or stopped taking your CV medication without telling your doctor, because you felt worse when you took it? (Check one)

Yes

No

4. When you travel or leave home, do you sometimes forget to bring along your high blood pressure medication? (Check one)

Yes

No

5. Did you take your CV medications yesterday? (Check one)

Yes

No

6. When you feel like your symptoms are under control, do you sometimes stop taking your CV medicine? (Check one)

Yes

No

7. Taking CV medication everyday is a real inconvenience for some people. Do you ever feel hassled about sticking to your treatment plan? (Check one)

Yes

No

8. How often do you have difficulty remembering to take all your CV medications? (Check one)

Never or rarely

Once in a while

Sometimes

Usually

All of the time

**Health Economics/Outcomes Research Methodological
Protocol: Appendix D**

Drug Substance Nexium, LDA

Study Code D961FC00004

Appendix Edition Number 1

**Appendix D
ePRO-EMA Diary Self Initiated Assessment**

ePRO-EMA Diary Self Initiated Assessment

Text	Response options
About your episode:	
How long ago did it end?	<1 minute, 2-5 minutes, >5 minutes
How long did it last?	0-480 minutes
Where were you most during the episode?	Home, Workplace, Other's home, Bar, Restaurant, Vehicle, Outside, Casino, Other
What were you doing during the episode?	Working/chores, Inactive/leisure, Interacting with others, Eating/drinking (15 min), Between activities, Other activities
Type of work?	Job, School, House/Personal, Other
Type of inactivity/leisure?	Media, Hanging out, Hobbies, Sports/Exercise, Reading, Waiting, Doing nothing, Other
Type of interaction with others?	Socializing, For business, Household issues, Arguing, Other interaction
What eating or drinking?	Meal, Snack, Caffeinated drink, Non-caffeinated drink, Alcohol
Thinking about your symptoms during the episode, how would you rate the following:	

A burning feeling behind your breastbone?	Did not have, Very mild, Mild, Moderate, Moderately sever, Severe
Pain behind your breastbone?	Did not have, Very mild, Mild, Moderate, Moderately sever, Severe

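### The evening diary labels its cardiovascular answers as heart only, so stroke/TIA and risk-factor medicines and visits have no answer that names them

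*Protocol*

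**What the plan says.** **Diary.** The Evening Assessment in Appendix D asks which medicines were taken since the last evening report, with the answers "Low dose aspirin, Other heart medication, GI medication". It then asks about doctor, emergency-room and hospital visits, and gives the reasons as "Heart related problems, GI problems, other".

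**Population.** Section 3.3.2.1 admits subjects with coronary disease and also those with "previous TIA (Transient Ischemic Attack) or ischemic stroke (secondary prevention), or subjects with known risk factors for cardiovascular disease" who have had no earlier event.

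**Objective.** Section 2 sets out to "Observe and record upper GI symptoms and compliance with LDA, and other relevant medications". It also names doctor's visits as an example of the behaviour to be documented.

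**Other stages.** Section 3.1 says the survey covers the effect of symptoms on "compliance with taking LDA and medications related to their CV disease or CV risk factors", and the interview covers "compliance with LDA and other CV related medication". The adherence scale in Appendix C, section 1.7, opens with "Do you sometimes forget to take your CV medications".

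**The concern.** The survey and the interview ask about cardiovascular medicines. The diary, which is the only prospective source, asks about heart medicines. A subject on treatment for blood pressure, lipids or a previous stroke, with no heart diagnosis, has no answer that clearly applies. The same holds for the reason given for a visit after a TIA or for blood-pressure control.

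At stake are two secondary uses of the diary. The first is any summary of compliance with medicines other than LDA. The second is any breakdown of visits by reason. Both would be incomplete for subjects whose cardiovascular condition is not cardiac. The information cannot be recovered at the analysis stage, because the question was not asked in a form that holds it.

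**Working it through.** No arithmetic applies: the protocol states no figure on this point. The check sets the passages side by side.

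1. **Is there another diary source for these medicines?** Table 3 marks medication usage at all four report types. In Appendix D the morning and afternoon forms carry no medication item. The self-initiated form asks only what was taken in response to an episode, and its options are acid suppressants, a drink or over-the-counter products. The evening item is therefore the only one that covers LDA or other cardiovascular medicines.

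2. **Is there another source for visits?** Table 3 places healthcare utilization in the evening report alone.

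3. **Does the CRF fill the gap?** Table 1 schedules concomitant medication at Visit 1 only. The CRF shows what a subject was on at entry. It does not show what was taken day by day or what was started later.

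4. **Is *heart* defined more widely anywhere?** No such definition appears. The abbreviation list explains CV as the cardiovascular system in general. Table 2 says the adherence scale was adapted from blood-pressure medication to CV medication, and one of its items still names blood-pressure medication. Within the survey, then, blood-pressure drugs count as CV medication.

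5. **What does a blank mean?** The medication item has no *none* and no *other*. A blank against the heart answer is compatible with three states: the medicine was not taken, none was prescribed, or the subject took one but does not call it a heart drug.

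6. **What is untouched?** LDA has its own answer in the medication item. GI problems have their own answer in the visit item. Type of visit and whether it was planned are recorded whatever the reason.

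7. **Size.** Section 3.1 as revised by Amendment 2 aims for diary data from 200 + 25 + 50 = 275 subjects. The protocol does not say how many of them would have no cardiac diagnosis, how many of those take a non-cardiac cardiovascular medicine, or how many would leave the heart answer blank. As far as the document goes, the number affected could be anything from 0 to 275.

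**The case against.** Several counter-arguments have force.

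- **Scope.** The phrases about CV disease and risk factors describe the survey and the interview. For the diary, section 3.1 and Table 3 speak only of medication use. This is correct: the diary breaks no stated diary scope. The mismatch is with the eligible population and with the study-wide objective, which covers medicines other than LDA but does not define which are relevant.
- **Lay reading.** Because the answer follows aspirin and begins with *Other*, it treats aspirin as a heart medicine and may invite a broad reading. Section 3.4.1.1 also provides standardized device training, and its materials are not shown. Some subjects may well tick the box for a blood-pressure drug. If some do and others do not, the item is inconsistent rather than repaired.
- **Planned analyses.** Section 6.2.2 focuses the diary analysis on the onset of upper GI symptoms and on change in LDA use. Section 6.2 rules out hypothesis tests of group differences. No compliance rate for non-LDA medicines is defined. This limits the consequence and stands.

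A reader might infer that the labels create a spurious compliance gap between cardiac and non-cardiac subjects, or between secondary and primary prevention, and might try to put a number on it. With true intake of 90% and 25% to 50% of non-cardiac subjects not ticking, the gap is 0.9 × 0.25 = 22.5 points to 0.9 × 0.5 = 45 points. The documents do not support this. All the inputs are assumed, the result merely restates the assumed rate of not ticking, and no such comparison is planned.

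**Conclusion.** The point holds in a limited form. Both cardiovascular answers in the evening diary are narrower than the population enrolled and narrower than the wording of the other two stages, and no text shown widens them. On a literal reading, non-cardiac cardiovascular visits are pooled with unrelated ones, and non-cardiac cardiovascular medicines are not captured.

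That these medicines would actually be recorded as missed is an inference. It depends on how subjects read the label and on how a later analysis treats a blank, and the protocol fixes neither. Nor does the protocol make visit reason or cardiovascular events a stated outcome, so a stroke visit filed under the residual answer loses its label but is still counted as a visit. The size cannot be calculated. The correction is nonetheless worth making, because it is cheap and the loss cannot be made good afterwards.

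**What to change.** **If the device can still be changed.** Use the protocol's cardiovascular wording with plain examples in both items:

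- Medication: *Other heart or cardiovascular medicine, such as for blood pressure, cholesterol or stroke prevention*. Add *none* and *other* to the list.
- Visit reason: *Heart, stroke/TIA, blood pressure or other cardiovascular problem*.

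Do not make the medication answer appear only when the CRF lists such a drug. Section 5 shows that the CRF is on paper and is held in a different database from the device data. Medicines started after Visit 1 would also lose their answer.

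**For data collected under the present labels.** Describe both items in tables and text as heart-specific, as worded. Limit any summary of non-LDA compliance to subjects whose Visit 1 CRF lists a cardiac drug, using a list of such drugs fixed before the diary data are tabulated. Do not present the result as compliance with cardiovascular medication in general. Drugs started after Visit 1 remain outside this summary.

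**Cost.** Two relabelled answers, two added options and the matching translations, or one analysis restriction using CRF data already collected. The drawback of relabelling is timing. Amendment 2 is dated 19 June 2008 and puts the end of diary enrolment at about 15 June 2008, so a change during or after enrolment would mix two wordings. In that case the analysis restriction is the remedy.
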